#### 6.2.2 Concomitant diseases and conditions

The number and percentage of study participants with concomitant diseases and conditions (medical history conditions noted as ongoing at study entry for the SP848 study), except epilepsy, will be summarized by SOC and PT for the SS.

## 6.3 History of epilepsy

The history of epilepsy uses CRF/eCRF information collected at the time of entry into the previous pediatric LCM study for those study participants who enrolled from SP847 (or other LCM pediatric clinical studies in epilepsy). The history of epilepsy will be obtained from the Screening Visit for those study participants who directly enrolled into SP848.

### 6.3.1 History of seizure types

The number and percentage of study participants experiencing partial-onset seizures (type I), simple partial (type IA), complex partial (type IB), and partial, secondary generalized seizures (type IC), in addition to each seizure category within such, at any time prior to study entry (into the previous study for rollover study participants or into SP848 for those direct enrollers) will be summarized based on the 1981 International League Against Epilepsy (ILAE) Seizure Classification History CRF/eCRF module. This will be summarized for the SS, by seizure classification subgroups.

For POS study participants the following classifications will be used. A subject will be classified as having a history of partial-onset seizures (I) if the subject has a history of simple partial (IA), complex partial (IB), or partial, secondary generalized (IC) seizures. A subject will be classified as having a history of simple partial seizures if the subject has a history of motor signs (IA1), somatosensory or special sensory symptoms (IA2), autonomic symptoms or signs (IA3), or psychic symptoms (IA4). A subject will be classified as having a history of complex partial seizures if the subject has a history of simple partial onset followed by impairment of consciousness with simple partial features (IB1a) or automatism (IB1b), or if the subject has a history of impairment of consciousness at onset with no other features (IB2a) or automatism (IB2b). A subject will be classified as having a history of partial, secondary generalized seizures if the subject has a history of simple partial evolving to generalized (IC1), complex partial evolving to generalized (IC2), or simple partial evolving to complex partial evolving to generalized (IC3) seizures.

For study participants with generalized seizures the following classifications will be used. A subject will be classified as having a history of partial-onset seizures (I) if the subject has a history of simple partial (IA), complex partial (IB), or partial, secondary generalized (IC) seizures. A subject will be classified as having a history of simple partial seizures if the subject has a history of motor signs (IA1), somatosensory or special sensory symptoms (IA2), autonomic symptoms or signs (IA3), or psychic symptoms (IA4). A subject will be classified as having a history of generalized seizures (II) if the subject has a history of absence (IIA), myoclonic (IIB), clonic (IIC), tonic (IID), tonic-clonic (IIE), or atonic (IIF) seizures. A subject may also be classified as having a history of unclassified epileptic seizures (III).

### 6.3.2 History of seizure characteristics

Quantitative summaries of epilepsy duration and age at diagnosis (as defined in Section 3.2.9) will be summarized for the SS. This will be summarized for the SS, by seizure classification subgroups.

### 6.3.3 Historical seizure counts

The Historical Seizure Counts CRF/eCRF module records the number of seizures per pre-selected ILAE seizure code experienced by the subject during the 4 weeks prior to Baseline.

These data will be provided in a subject data listing. This will be summarized for the SS, by seizure classification subgroups.

## **6.4 Prior and concomitant medications**

All prior and concomitant medications will be presented by seizure classification subgroup, age group, weight band and overall. Antiepileptic drugs defined as medications documented on the “Concomitant Medications (AEDs only)” log form. A medical review will be performed to ensure that the medications are documented correctly. A listing of all medications taken during the study will be presented.

### **6.4.1 Number of previous AEDs**

The number of previous AEDs defined as AEDs taken and stopped >28 days prior to entry into the study, will be summarized for the SS based on the following categorization: 0 AED, 1-3 AEDs, 4-6 AEDs, and  $\geq 7$  AEDs. This summary will be based on the History of Previous AED Treatment CRF/eCRF module for applicable studies which only includes AEDs stopped prior to study entry. For study participants who rolled over from the SP0966 study, previous AEDs are defined as AEDs taken 12 months prior to informed consent date and stopped >28 days prior to entry into SP0966.

### **6.4.2 Concomitant AEDs taken at the start of the SP848 Treatment Period**

Concomitant AEDs taken at the start of the SP848 Treatment Period are defined as AEDs taken concomitantly with LCM at the time of first dose of LCM in SP848.

The number of concomitant AEDs taken at the start of the SP848 Treatment Period will be summarized for the SS based on the following categorization: 0 AED, 1 AED, 2 AEDs, 3 AEDs and  $\geq 4$  AEDs. The number and percentage of study participants taking concomitant AEDs at the start of the SP848 Treatment Period will be summarized overall and, separately, by WHODD chemical subgroup (level 4) and preferred drug name, for the SS.

### **6.4.3 Concomitant AEDs taken during the SP848 Treatment Period**

Concomitant AEDs taken during the SP848 Treatment Period are defined as AEDs taken concomitantly for at least one day in common with LCM in SP848.

The number and percentage of study participants taking concomitant AEDs during the SP848 Treatment Period will be summarized overall and, separately, by WHODD chemical subgroup (level 4) and preferred drug name, for the SS.

VNS is allowed and will not be counted as a concomitant AED.

### **6.4.4 Concomitant medications (excluding AEDs)**

The number and percentage of study participants taking concomitant non-AEDs during the SP848 Treatment Period will be summarized overall and, separately, by WHODD anatomical main group (level 1) and therapeutic subgroup (level 2), for the SS.

## **7 MEASUREMENTS OF TREATMENT COMPLIANCE**

Information reported on the eCRF regarding LCM dispensed and returned will be reported in subject data listings. No summaries of these results are planned. LCM dosing compliance will be

evaluated through the review of important protocol deviations classified under LCM Dosing Regimen (see Section 3.4).

## 8 SAFETY ANALYSES

All safety variables will be analyzed by descriptive methods for the SS.

### 8.1 Extent of exposure

All the summaries described below will also be presented by seizure classification subgroup, using the levels defined in Section 3.2.7, and for the FAS.

The duration of LCM exposure (days), as defined in Section 3.2.7, will be summarized as a continuous parameter (in days) overall, and repeated by weight band using the levels defined in Section 3.2.10. In addition, the duration of LCM exposure will be summarized using the cumulative 6-month time intervals for the Treatment Period, as defined in Section 3.2.7.

Subject-years of LCM exposure will be summarized using the cumulative 6-month time intervals for the Treatment Period, as defined in Section 3.2.7.

The maximum daily LCM dose (mg/kg/day), as defined in Section 3.2.8, will be summarized overall, and repeated by weight band using the levels defined in Section 3.2.10.

The modal daily LCM dose (mg/kg/day), as defined in Section 3.2.8, will be summarized, overall, and repeated by weight band using the levels defined in Section 3.2.10. In addition, the number of study participants and subject-years exposed in each of the modal daily LCM dose categories (mg/kg/day) will be summarized for the Treatment Period, as defined in Section 3.2.8.

Summary statistics (n, mean, SD, minimum and maximum) for the duration of LCM exposure (days) and median daily LCM dose (mg/kg/day) during each of the following analysis periods for direct enrollers: Titration, Post-Titration and Treatment Period will be summarized for the SS. Duration of LCM exposure (days) and median daily LCM dose (mg/kg/day) for the Treatment Period will be summaries for the rollover and all study participants in the SS separately.

### 8.2 Adverse events

AEs will be tabulated by MedDRA SOC and MedDRA PT; select tables will also be presented by weight band and seizure classification subgroup using the levels defined in Sections 3.2.10 and 3.2.12, respectively. Additional tables will also be presented by time interval using the definition in Section 3.2.5. The number and percentage of study participants experiencing each event at least once will be summarized. All summaries will be sorted alphabetically by SOC and by frequency of events within PTs, starting with the most frequent event overall.

AEs will be classified as pre-treatment, treatment-emergent, or post-treatment. Pre-treatment AEs are defined as AEs which had an onset date prior to the first SP848 dose of LCM.

Treatment-emergent AEs (TEAEs) are defined as those events which started on or after the date of first SP848 dose of LCM, or whose intensity worsened on or after the date of first SP848 dose of LCM. AEs occurring within 30 days after last dose of LCM will be considered treatment emergent. Post-treatment AEs are defined as AEs which had an onset date after 30 days after the last dose of LCM.

For results disclosure on public registries (eg, ClinicalTrials.gov), treatment-emergent adverse events and treatment-emergent serious adverse events will be published.

All AEs reported during the study including pre-treatment and post-treatment AEs will be provided in a subject data listing.

An overview of the incidence of TEAEs will provide the overall summary of TEAEs and the numbers and percentages of study participants with at least 1 TEAE, with a serious TEAE, with a drug-related TEAE, with a severe TEAE, and with a drug-related serious TEAE. The number and percentage of subject discontinuations due to TEAEs, the number and percentage of all deaths (if applicable), and the number and percentage of study participants with AEs leading to death (if applicable) will also be summarized. This overall summary will be repeated by weight band and seizure classification subgroup using the levels defined in Sections 3.2.10 and 3.2.12 respectively. In addition, the overall summary will be presented for the Titration Period, Post-Titration Period and Treatment Period for the direct enrollers and the Treatment Period for the rollover study participants.

The following summaries of AEs will be provided by MedDRA primary SOC and PT:

- Incidence of TEAEs
- Incidence of TEAEs with onset during the Titration Period for direct enrollers
- Incidence of TEAEs with onset during the Post-Titration Period for direct enrollers
- Incidence of TEAEs with onset during the Treatment Period for direct enrollers
- Incidence of TEAEs for direct enrollers
- Incidence of TEAEs for rollover study participants
- Incidence of serious AEs
- Incidence of serious TEAEs
- Incidence of non-serious TEAEs
- Incidence of TEAEs leading to discontinuation from the study
- Incidence of TEAEs by relationship to LCM
- Incidence of TEAEs by maximum intensity
- Incidence of TEAEs related to Potentially Drug Induced Liver Injury (PDILI) (defined in Appendix 12.3)
- Incidence of pediatric growth-, neurodevelopment-, behavior-, and endocrine-related TEAEs (defined by manual medical review)
- Incidence of non-serious TEAEs by relationship to LCM
- Incidence of fatal TEAEs by relationship to LCM
- Incidence of non-serious TEAEs occurring in at least 5% of study participants
- Incidence of non-serious TEAEs occurring in at least 5% of study participants by relationship to LCM

- Incidence of drug-related TEAEs by seriousness
- Incidence of other significant TEAEs (defined in Appendix 12.2).

The following summaries of AEs will also be repeated by weight band and seizure classification subgroup using the levels defined in Sections 3.2.10 and 3.2.12, respectively.

- Incidence of TEAEs
- Incidence of serious AEs
- Incidence of serious TEAEs
- Incidence of TEAEs leading to discontinuation from the study
- Incidence of non-serious TEAEs occurring in at least 5% of study participants
- Incidence of drug-related TEAEs by seriousness
- Incidence of other significant TEAEs (defined in Appendix 12.2).

The following summaries of AEs will be presented for the time intervals (using the definition in Section 3.2.5) of:  $\leq 3$  months,  $> 3$  to  $\leq 6$  months,  $> 6$  to  $\leq 9$  months,  $> 9$  to  $\leq 12$  months,  $> 12$  to  $\leq 15$  months,  $> 15$  to  $\leq 18$  months,  $> 18$  to  $\leq 21$  months,  $> 21$  to  $\leq 24$  months, and  $> 24$  to  $\leq 30$  months,  $> 30$  to  $\leq 36$  months,  $> 36$  to  $\leq 42$  months,  $> 42$  to  $\leq 48$  months,  $> 48$  months:

- Incidence of all TEAEs with onset during the Treatment Period
- Incidence of all serious AEs with onset during the Treatment Period
- Incidence of all serious TEAEs with onset during the Treatment Period
- Incidence of all TEAEs leading to discontinuation from the study with onset during the Treatment Period
- Incidence of all other significant TEAEs with onset during the Treatment Period (defined in Appendix 12.2)

In addition, summaries for the incidence of TEAEs overall, incidence of serious AEs, incidence of serious TEAEs, incidence of TEAEs leading to discontinuation from study, incidence of other significant TEAEs, TEAEs related to PDILI, and pediatric growth-, neurodevelopment-, behavior-, and endocrine-related TEAEs will be repeated presenting the site and subject number of all those study participants experiencing each TEAE as well as in subject data listings.

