#### **2.4.1.2 Study participants enrolling directly into SP848**

Beginning with Protocol Amendment 4, at selected sites, up to approximately 100 eligible pediatric study participants  $\geq 4$  years to  $\leq 17$  years of age with partial-onset seizures (deemed appropriate for treatment with adjunctive LCM) who have not previously received LCM will be permitted to enroll directly into SP848.

Beginning with local Protocol Amendment 5.2 for sites in Japan, approximately 46 eligible pediatric subjects  $\geq 4$  years to  $\leq 17$  years of age with partial-onset seizures who have not previously received LCM will be permitted to directly enroll at approximately 9 sites in Japan. Beginning with Protocol Amendment 5.4 for sites in China, approximately 60 additional eligible pediatric subjects with partial-onset seizures aged  $\geq 4$  years to  $\leq 17$  years, who have not previously participated in a LCM clinical study, will directly enroll into SP848.

Subjects who enroll directly into SP848 without previous participation in a LCM clinical study will undergo screening. Eligible subjects will initiate treatment with LCM, and the LCM dose will be titrated to a level to optimize tolerability and seizure control. Subjects will be able to

receive LCM oral solution or LCM tablets for up to 2 years as determined appropriate by the investigator.

SP848 includes subjects  $\geq 1$  month to  $\leq 18$  years of age since subjects who complete SP847 or another applicable LCM pediatric epilepsy study in subjects  $< 18$  years of age may have aged to 18 years old by the time they complete that study and enroll in SP848.

The same study conditions described in Section 2.4.1.1 (e.g., minimum and maximum LCM dose, required office visits for dose increases, concomitant AEDs, and LCM taper) also apply.

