#### Treatment Period

This is defined as the period of time from the date of first dose of LCM in SP848 to the latter of the last LCM dose date and the study Termination Visit (ie, Early Termination Visit) date.

The Treatment Period is further broken down into the Titration Period and the Post-Titration Period for direct enrollers:

- Titration Period: defined as the date of the first dose of study medication to the day prior to date of Visit 1 or the date of Early Termination (ET) visit in the situation where a subject discontinues prior to the last visit in the Titration Period.
- Post-Titration Period: defined as the date of Visit 1 to the end of the Treatment Period.

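### For direct enrollers, crude TEAE percentages are shown side by side for two periods of very unequal length, so the tables can hide a several-fold higher event rate during Titration

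*SAP*

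**What the plan says.** SAP Section 8.2 fixes the measure for adverse events: "The number and percentage of study participants experiencing each event at least once will be summarized". For direct enrollers, "the overall summary will be presented for the Titration Period, Post-Titration Period and Treatment Period for the direct enrollers", and the tables by system organ class and preferred term include "Incidence of TEAEs with onset during the Post-Titration Period for direct enrollers", with a matching table for Titration. No rate per unit of person-time is planned.

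Section 3.2.2 sets the boundaries: "Titration Period: defined as the date of the first dose of study medication to the day prior to date of Visit 1" (or the early termination visit for those who stop sooner) and "Post-Titration Period: defined as the date of Visit 1 to the end of the Treatment Period". Section 2.4.1.2 lets direct enrollers "receive LCM oral solution or LCM tablets for up to 2 years". Section 3.2.3 allows Japanese participants to stay longer. The SAP gives no length for Titration in weeks.

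Three other provisions bear on the point:

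- Section 8.1 reports exposure days and median daily dose over "analysis periods for direct enrollers: Titration, Post-Titration and Treatment Period will be summarized for the SS". Subject-years are planned only by cumulative 6-month interval and by modal dose.
- Section 8.2 tabulates TEAEs in 3-month intervals (84 days, by Section 3.2.5) up to 24 months. A participant counts in an interval if exposed at any time in it.
- On population and denominator, Section 8 says "All safety variables will be analyzed by descriptive methods for the SS". Section 3.1 leaves each denominator to whichever number of participants suits the analysis.

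**The concern.** The chance of having at least one event rises with time under observation. Two such percentages taken over very different lengths of time do not show in which period the event rate was higher. Once TEAEs are split at the end of Titration, readers will naturally use the columns to ask whether risk sits in the initiation phase. Under ordinary conditions the columns can answer that question the wrong way round.

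TEAE incidence and withdrawal due to TEAEs are primary safety variables (Section 2.3.1). Direct enrollers were added for long-term safety data intended for planned marketing applications (Section 2.5). They are also the group in which starting LCM is most clearly visible, because rollover participants begin SP848 on the dose they were already receiving (Section 2.4.1.1).

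**Working it through.** The SAP states no event rate, dropout rate or titration length for this point, so there is no planned figure to reproduce. What follows is an illustration.

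**Inputs**

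- From the SAP: the period boundaries (3.2.2), a maximum of 2 years (2.4.1.2), and a 28-day month (3.2.5).
- Assumed: Titration of 4, 6, 8 or 12 weeks; a constant event rate within each period; Post-Titration rates λ of 0.05, 0.2 and 1.0 per subject-year; dropout over Post-Titration of 0%, 30% or 50%.

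**Model.** Let t and T be the lengths of Titration and Post-Titration in years, R the ratio of the Titration rate to the Post-Titration rate, and d the dropout hazard.

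- Titration: P = 1 − exp(−λRt)
- Post-Titration: P = [λ/(λ+d)] × [1 − exp(−(λ+d)T)]
- Without dropout the two percentages are equal when R = T/t, whatever λ is.

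**Break-even ratio, 2 years (730.5 days) in total, no dropout**

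- 4 weeks: 702.5/28 = 25.1
- 6 weeks: 688.5/42 = 16.4
- 8 weeks: 674.5/56 = 12.0
- 12 weeks: 646.5/84 = 7.7

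**Percentages with at least one event, λ = 0.2, no dropout**

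| Titration | Titration %, R = 5 | Titration %, R = 10 | Post-Titration % |
|---|---|---|---|
| 4 weeks | 7.4 | 14.2 | 31.9 |
| 6 weeks | 10.9 | 20.5 | 31.4 |
| 8 weeks | 14.2 | 26.4 | 30.9 |
| 12 weeks | 20.5 | 36.9 | 29.8 |

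For 6 weeks and R = 5: 1 − exp(−0.2 × 5 × 42/365.25) = 10.9%, against 1 − exp(−0.2 × 688.5/365.25) = 31.4%. The underlying rates are 100 and 20 per 100 subject-years, the opposite order.

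**What weakens the effect**

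- With 50% dropout over Post-Titration, the break-even ratio falls to 14.9–18.0 (4 weeks), 9.8–11.7 (6), 7.2–8.6 (8) and 4.7–5.5 (12), depending on λ. A 3- to 4-fold higher Titration rate still gives the lower percentage in every 2-year scenario tried.
- With a 6-week titration and only 84 days of Post-Titration follow-up, break-even is 84/42 = 2.
- With R = 10 and a 12-week titration, the percentages stand in the right order (last row of the table).

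**What the 3-month tables would show** (6-week titration, λ = 0.2, R = 5)

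- Direct enrollers alone, first 84 days: 1 − exp(−0.2 × (5 × 42 + 42)/365.25) = 12.9%. A later 84 days: 1 − exp(−0.2 × 84/365.25) = 4.5%. The ratio is 2.9.
- Pooled: reading the Section 2.5 figures as additive, direct enrollers are about 100 + 46 + 60 = 206 of about 400, or 51.5%. If all others carry the background rate throughout, the first interval shows 0.515 × 12.9 + 0.485 × 4.5 = 8.8% against 4.5%, a ratio of 2.0. The signal is diluted but not lost.

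**The case against.** The strongest reply is that the plan compares nothing. Section 3.1 makes every summary descriptive with no hypothesis test, and Section 8.2 only presents the periods. Section 8.2 also already contains a better tool. The 3-month tables have equal interval length up to 24 months and an exposed denominator, and they cover TEAEs, serious TEAEs, TEAEs leading to discontinuation and other significant TEAEs. A 4- to 8-week titration would fall wholly inside the first interval. Section 8.1 gives n and mean exposure days for each period, so crude person-time can be worked out by hand.

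Much of this stands. A reader might infer that the SAP sets up a comparison of the periods, or that its tables will always make Titration look safer. Neither is supported: no comparison or purpose is stated, the weeks and event rates used here are assumptions, and the reversal depends on the rate ratio lying below the duration ratio. A reader might also infer from the Safety Set wording in Section 8 that children who left during Titration must be counted in the Post-Titration denominator. Section 3.1 allows a suitable denominator, so this is missing detail, not an error.

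What the reply does not remove is this. Exposure sits in other tables, and it is total exposure, not time to first event. The interval tables are planned overall and by age group, not for direct enrollers alone, and they are not aligned to Visit 1. They omit drug-related and severe TEAEs, which the by-period overview includes. Having no test does not make a misleading descriptive table clearer.

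**Conclusion.** The point holds in a limited form. The by-period TEAE tables for direct enrollers use crude percentages over very unequal periods, and they can show less in Titration when the rate there is several times higher. Over 2 years without dropout, equality of the percentages needs a Titration rate about 8 to 25 times higher (12 down to 4 weeks of titration); with 50% dropout it needs about 5 to 18 times. These figures rest on constant rates within each period and on assumed titration lengths, and they shrink with short follow-up. The existing exposure and interval tables mitigate the problem without curing it. This is an inexpensive improvement to the presentation of primary safety data, not a fault that invalidates the planned analysis.

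**What to change.** In SAP Section 8.2:

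1. In the Titration/Post-Titration overview for direct enrollers, add subject-years at risk and the number of participants with an event per 100 subject-years. Count time to first event or end of period. Do this for any TEAE, serious TEAE, TEAE leading to discontinuation, drug-related TEAE and other significant TEAEs (the last needs a new row).
2. Match the at-risk window to the window in which onsets are counted. Exposure ends at last dose (3.2.7), the Treatment Period may run to the termination visit (3.2.2), and TEAEs are counted to 30 days after last dose (8.2). Numerator and person-time must stop at the same date.
3. Repeat the existing 3-month interval TEAE tables for direct enrollers only.
4. For clarity, state that the Post-Titration denominator is direct enrollers who reached Visit 1.

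Cost: the period dates are already needed for Section 8.1, but its exposure totals are not enough. Time to first event must be derived separately for each event class, and the tables become longer. No new data are needed.
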